9.6. Pharmacodynamics

See Section 10.3.3.

9.7. Genetics

Genetics are evaluated in this study.

A 6 mL blood sample for deoxyribonucleic acid (DNA) isolation will be collected on Day 1 from participants who have consented to participate in the genetics analysis component of the study. Participation is optional. Participants who do not wish to participate in the genetic research may still participate in the study.

In the event of DNA extraction failure, a replacement genetic blood sample may be requested from the participant. Signed informed consent will be required to obtain a replacement sample unless it was included in the original consent.

See [Appendix 6](#) for Information regarding genetic research. Details on processes for collection and shipment and destruction of these samples can be found in the laboratory manual and the SRM.

9.8. Biomarkers

Viral Genotyping and Phenotyping

Whole venous blood samples will be obtained from each participant to provide plasma for viral genotype and phenotype analysis, at the times listed in the SOA (Section 2). Details concerning the handling, labeling and shipping of these samples will be supplied separately.

Genotypic and phenotypic analyses will be carried out by using Gag/PR and PR/RT formats, in which PCR amplification is used to generate HIV cDNA products including the Gag and the PR and RT coding regions, respectively. Phenotypic analyses of the Gag/PR region will include susceptibility to GSK3640254. Analysis will be done on samples collected in study Part 1 on Day 1 and Day 11 initially, and on samples collected in study Part 2 on Day 1 and Day 8 initially, with other timepoints analyzed as data emerge for viral load response.

9.9. Health Economics OR Medical Resource Utilization and Health Economics

Health Economics/Medical Resource Utilization and Health Economics parameters are not evaluated in this study.

10. STATISTICAL CONSIDERATIONS

10.1. Sample Size Determination

10.1.1. Sample Size Considerations

The primary objectives of this study are to investigate the safety, tolerability and antiviral activity of GSK3640254 over a 10-day treatment period in study Part 1 and over a 7-day treatment period in study Part 2. The antiviral activity will be assessed by estimating plasma HIV-1 RNA max change from baseline during the study.

The sample size for this study is based primarily on feasibility to provide adequate precision for the estimations.

Based on data from the short-term monotherapy study of BMS-955176/GSK3532795 POC (AI468002) study and GSK2838232 POC study, we assumed the maximum change from baseline viral load drop (VLD) values on log scale for individual participants from the higher dose in Part 1 follow a normal distribution. Therefore, we conducted 1000 trial

simulations in Fixed and Adaptive Clinical Trial Simulation (*FACTS*) software using the normal distribution with mean of change from baseline VLD on log scale at 0.5 to 2 copies, SD=0.4, and sample sizes=6 for Part 1 higher dose.

Using Bayesian calculation with non-informative priors for the mean and weakly informative priors for the error parameters, Normal (0, 100) for mean and Inverse Gamma (0.35, 0.0875) for error parameters, the posterior probability to achieve a clinically relevant cut-point of 1.3 log was calculated for each simulated trial, and percentage of the trials with posterior probability of mean viral load drop (VLD) at the higher dose in Part 1 >1.3 log (given the true mean VLD on log scale) $\geq 20\%$ was calculated and are shown below in [Table 5](#).

Table 5 Percentage of the trials with posterior probability $\geq 20\%$ for Part 1 higher dose using sample size=6

True Mean VLD on log scale	Posterior Probability $\geq 20\%$	Posterior Probability $< 20\%$
0.5	0.0%	100.0%
0.7	0.1%	99.9%
0.8	0.6%	99.4%
0.9	4.6%	95.4%
1	15.0%	85.0%
1.1	35.9%	64.1%
1.2	60.8%	39.2%
1.3	81.8%	18.2%
1.4	92.4%	7.6%
1.5	97.9%	2.1%
1.6	99.8%	0.2%
1.7	100.0%	0.0%
2	100.0%	0.0%

The precision of the dose response curve (with sample size N=6) is provided in [Table 1](#) (Section [5.5.1](#)).

10.1.2. Sample Size Sensitivity

Similar simulations in *FACTS* were conducted using sample sizes of 8 for Part 1 higher dose. Using Bayesian calculation, the posterior probability to achieve a cut-point 1.3 log was calculated for each simulated trial, and percentage of the trials with posterior probability greater than or equal to 20% was calculated (given the true mean VLD on log scale) and are shown below in [Table 6](#).

Table 6 Percentage of the trials with posterior probability $\geq 20\%$ for Part 1 higher dose using sample size=8

True Mean VLD on log scale	Posterior Probability $\geq 20\%$	Posterior Probability $< 20\%$
0.5	0.0%	100.0%
0.7	0.0%	100.0%
0.8	0.6%	99.4%
0.9	2.5%	97.5%
1	10.2%	89.8%
1.1	27.4%	72.6%
1.2	56.2%	43.8%
1.3	81.3%	18.7%
1.4	93.8%	6.2%
1.5	98.9%	1.1%
1.6	99.8%	0.2%
1.7	100.0%	0.0%
2	100.0%	0.0%

Compared with the results of sample size=6 in [Table 5](#), we only found slightly difference for the operation characteristics. It would be sufficient using sample size=6 for the interim analysis Go/No Go decision making.

10.1.3. Sample Size Re-estimation or Adjustment

No sample size re-estimation will be performed.

10.2. Populations for Analyses

Intent to Treat Exposed Population (ITT)

The ITT-Exposed Population is defined as all participants who meet study criteria and are enrolled into the study with documented evidence of having received at least 1 dose of treatment and at least one post-baseline HIV-1 RNA measurement. This will be the primary population for the final efficacy analysis for all active treatment groups.

Per Protocol Population (PP)

The Per Protocol Population is defined as all participants who meet study criteria and are enrolled into the study with documented evidence of having received all doses and all post-baseline HIV-1 RNA measurement, with exceptions of major protocol deviation.

Safety Population

The Safety Population is defined as all participants who are enrolled into the study with documented evidence of having received at least 1 dose of randomized treatment.

Pharmacokinetic Population

The PK Population will include all participants who receive GSK3640254 and undergo plasma PK sampling during the study. Participants for whom a plasma PK sample is obtained and assayed will be included in the listing of plasma GSK3640254

concentration-time data. Results from samples collected from a participant with emesis occurring within 2 hours of the dose will not be considered as evaluable.

10.3. Statistical Analyses

10.3.1. Interim Analysis

An informal unblinded interim analysis of preliminary safety, tolerability, PK and antiviral activity will occur after participants of Part 1 complete their Day 12 visit. If the review of Part 1 highest dose shows that exposures are similar or higher than observed with 200 mg QD in healthy participants, this dose will be the highest dose in this study and only in this case, the Bayesian posterior probability (based on Part 1 higher dose data) that the log₁₀ mean VLD from baseline is greater than a cut-point=1.3 log will be calculated for the Go/No Go decision for Part 2:

- If the probability is less than 20%, the trial will not move forward into Part 2 (No Go decision).
- Otherwise, the study team will review the whole Part 1 data in order to make a dose selection decision for the subsequent Part 2 cohorts

The study team will review the safety, tolerability, PK and antiviral activity data in order to confirm the dose selection for Part 2 cohorts. If the exposure to GSK3640254 200mg (Part 1 higher dose) looks similar or higher to those obtained with 200 mg QD in healthy volunteers in prior studies, and the effect observed at the Part 1 low dose is as anticipated, the Part 2 doses will be as initially planned as described in Section 5.5.2. If the exposure to GSK3640254 200mg are significantly lower than what anticipated (e.g. lower by at least 25%), the new highest dose predicted to provide a 200 mg equivalent exposure will be estimated and proposed for Part 2. The team will evaluate and possibly run the same Bayesian criteria to test the projected new highest dose VL drop in the interim analysis. If the effect observed with the Part 1 low dose is not as anticipated, the PK/PD model may be refined, and the Part 2 target effects and doses may be updated.

Maximum change and change from baseline in plasma HIV-1 RNA will be summarized by treatment or by visit. The analyses will be done for both PP and ITT exposed population if two populations are not the same.

10.3.2. Primary Analyses

The final analysis will be performed after the completion of the study and final datasets authorization. Data will be listed and summarized according to GSK reporting standards, where applicable. Listings will be sorted by participant, period, day, and time, noting treatment; summaries will be presented by treatment, visit/day, and time. Unless stated otherwise, descriptive summaries will include n, mean, standard deviation (SD), coefficient of variation (%CV), median, minimum, and maximum, geometric mean with associated 95% confidence interval (CI), and %CVb for continuous variables, whereas n and percent will be used as summary statistics for categorical variables. Baseline or pre-dose assessment is the last available assessment prior to time of the first dose unless it is specified otherwise. If there are multiple assessments collected on the same scheduled time, the average of these assessments will be used. For tabulated safety summaries, only

the scheduled assessments will be included in the summary tables. Version 9.1 or higher of the SAS system will be used to analyze the data as well as to generate tables, figures, and listings. Complete details will be documented in the Reporting and Analysis Plan (RAP).

10.3.2.1. Safety Analyses

Safety data will be presented in tabular format and summarized descriptively according to GSK's Integrated Data Standards Library standards and data will be in Clinical Data Interchange Standards Consortium (CDISC) format. No formal statistical analysis of the safety data will be conducted.

10.3.2.2. Efficacy Analyses

Both the PP and ITT Populations will be used for all efficacy analyses if there are dropouts. Plasma HIV-1 RNA max change and change from baseline during the study will be calculated for each participant and on each assessment visit/day.

Plasma HIV-1 RNA will be listed by treatment, participant, and assessment visit/day and summarized by treatment and assessment visit along with change from baseline.

Plots of mean and median plasma HIV-1 RNA actual and change from baseline data will be generated by treatment and assessment visit.

- Plasma HIV-1 RNA change from baseline to the nadir (maximum change from baseline) will be calculated for each participant and summarized by treatment.

Together, the data from Parts 1 and 2 will investigate the complete dose-exposure-response curve and the impact of lower doses/exposures on potential development of resistance.

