2.2. Part 1 and Part 2 Treatment, Post-Dosing and Follow-up Periods

Study Part 1:

Procedure ¹	Treatment Period Day 1 – Day 10									Post-Dosing Follow Up Period Day 11 – 17			Final Follow-up Day 18-24	
	Day 1	Day 2	Day 3, 4 Choose one day for the Clinic Visit 3. The other day will be a virtual event.		Day 5, 6, 7 Choose one day for the Clinic Visit 4. The other days will be virtual events.			Day 8, 9, 10 Choose one day for the Clinic Visit 5. The other days will be virtual events.			Day 11	Day 12	Day 13, 14, 15, 16 or 17	Day 18, 19, 20, 21, 22, 23 or 24
	Clinic Visit 1	Clinic Visit 2	Clinic Visit 3	Virtual	Clinic Visit 4	Virtual	Virtual	Clinic Visit 5	Virtual	Virtual	Clinic Visit 6	Clinic Visit 7	Clinic Visit 8	Clinic Visit 9
Clinical Assessments														
Outpatient Visit ²	X	X	X		X			X			X	X	X	X
Video/Phone Call				X		X	X		X	X				
Verify Inclusion/Exclusion Criteria	X													
Medical/medication/drug/alcohol history	X													
Prior Anti-retroviral (ARV) Check	X													
CDC Classification	X													X

Procedure ¹	Treatment Period Day 1 – Day 10										Post-Dosing Follow Up Period Day 11 – 17			Final Follow-up Day 18-24
	Day 1	Day 2	Day 3, 4 Choose one day for the Clinic Visit 3. The other day will be a virtual event.		Day 5, 6, 7 Choose one day for the Clinic Visit 4. The other days will be virtual events.			Day 8, 9, 10 Choose one day for the Clinic Visit 5. The other days will be virtual events.			Day 11	Day 12	Day 13, 14, 15, 16 or 17	Day 18, 19, 20, 21, 22, 23 or 24
	Clinic Visit 1	Clinic Visit 2	Clinic Visit 3	Virtual	Clinic Visit 4	Virtual	Virtual	Clinic Visit 5	Virtual	Virtual	Clinic Visit 6	Clinic Visit 7	Clinic Visit 8	Clinic Visit 9
HIV-associated conditions assessments ³	X	X	X	X	X	X	X	X	X	X	X	X	X	X
Adverse event (AE)/SAE assessment ³	X	X	X	X	X	X	X	X	X	X	X	X	X	X
Concomitant medication review ³	X	X	X	X	X	X	X	X	X	X	X	X	X	X
Weight, BMI and Physical exam ⁴	X													
Vital Signs	X	X	X					X						X
C-SSRS Administration (Since Last Visit form)											X			

Procedure ¹	Treatment Period Day 1 – Day 10									Post-Dosing Follow Up Period Day 11 – 17			Final Follow-up Day 18-24	

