10.3.3. Secondary Analyses

10.3.3.1. Pharmacokinetic/Pharmacodynamic Analyses

Relationships between various PK parameters (e.g., AUC, C_{max}, C_τ, etc.) and PD measures (e.g., maximum log₁₀ reduction from baseline in plasma HIV-1 RNA or safety parameters) will be explored using various models including E_{max}. The relationship between dose and PD measures will also be explored.

Details of the PK/PD exploratory analyses will be provided in the RAP.

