10. PHARMACODYNAMIC ANALYSES

10.1. Primary Pharmacodynamic Analyses

Relationships between dose and PD measures (maximum change (in Day 1 to Day 8) in log₁₀ plasma HIV-1 RNA from baseline) will be explored with an Emax and linear models. Part 1 and Part 2 doses combined in the model fitting. Model selection will be based on Akaike Information Criteria (AIC) value, where model with the lowest AIC value will be considered the best model.

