10.1.4. Statistical Analyses / Methods

Details of the planned displays are provided in [Appendix 11](#): List of Data Displays and will be based on GSK Data Standards and statistical principles.

Unless otherwise specified, endpoints / variables defined in Section [10.1.1](#) will be summarised using descriptive statistics, graphically presented (where appropriate) and listed.

Descriptive Summary tables are separated for Part 1 and Part 2 while the summary table for statistical modelling results are combined for two Parts.

In endpoint descriptive summary tables, the maximum change from baseline includes all visits while in model fitting it only includes visits from baseline to Day 8 in HIV-1 RNA for both parts.

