11.1.2. Population of Interest

The primary pharmacodynamics analyses will be based on the PK/PD population, unless otherwise specified. Part 1 Day 9~11 HIV RNA are excluded to fulfil the same dosing days and be used in one statistical model.

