13.11.11. Pharmacodynamic Tables

Pharmacodynamic: Tables					
No.	Population	IDSL / Example Shell	Title	Programming Notes	Deliverable [Priority]
PD Linear and Emax Models					
5.1.	PP	PD_T1	Summary of Estimates from Dose-Response Model	Only include visits from Day 1 to Day 8 for the HIV-RNA change. Part 1 and Part 2 doses all included in the statistical mode.	SAC

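### Cutting the modelled nadir at Day 8 equalises dosing days but not RNA sampling, so the pooled response models favour the Part 2 doses by an amount set by the Part 1 visit days

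*Protocol*

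**What the plan says.** Protocol 10.3.2.2 defines the nadir for the by-treatment summary, with no cut-off day: "Plasma HIV-1 RNA change from baseline to the nadir (maximum change from baseline) will be calculated for each participant and summarized by treatment". Protocol 10.3.3.1, on relating PK and dose to the maximum reduction, sets no cut-off either.

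The SAP adds one for modelling only. Section 10.1 pools the parts: "Part 1 and Part 2 doses combined in the model fitting". Section 10.1.4 separates two uses of the nadir. For description, "In endpoint descriptive summary tables, the maximum change from baseline includes all visits"; but "in model fitting it only includes visits from baseline to Day 8 in HIV-1 RNA for both parts". Section 11.1.2 gives the reason for the exposure-response model: "Part 1 Day 9~11 HIV RNA are excluded to fulfil the same dosing days and be used in one statistical model". The programming note for Table 5.1 repeats the rule: "Only include visits from Day 1 to Day 8 for the HIV-RNA change".

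Section 10.1.4.1 names the observed maximum change as the Emax response. Change from baseline to Day 8 is listed beside it (10.1.1, 10.1.4.1, 11.1.1, 11.1.3). The models contain no term for study part.

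The sampling days come from the Schedule of Activities (Protocol 2.2). In Part 1, Visit 5 may be on Day 8, 9 or 10: "Choose one day for the Clinic Visit 5. The other days will be virtual events". In Part 2, Visits 5 and 6 are fixed at Days 7 and 8.

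**The concern.** A nadir is an extreme value. Its expected size depends on how many noisy samples it is chosen from and on how late the last of them falls. The Day 8 cut leaves both unequal between the parts, and part is aligned with dose: 10 and 200 mg come only from Part 1, and 40, 80 and 140 mg only from Part 2. Part of the modelled difference between doses would then reflect the visit schedule and not the drug. Protocol 3.1 says the study's data will be used to choose Phase 2b doses, and the pooled models are where the five doses are put on one scale.

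**Working it through.** **The plan's own figure.** The only operating characteristic given for the maximum-change endpoint is Protocol Table 5: with a true mean of 1.3, SD 0.4 and n=6, 81.8% of trials reach a posterior probability of at least 20%. Simulating the stated priors gives 81.2% with an independent prior on the mean and 79.1% with the conjugate form. So n=6 and SD 0.4 are read correctly. The documents give no figure for the pooled models.

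**Sample counts to Day 8.** Part 2 has Days 2, 3/4, 5/6, 7 and 8: always five. In Part 1, nine combinations of Visit 3, 4 and 5 days meet the rule that visits on treatment are at most three days apart:

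| Visit 5 | Visit 3, 4, 5 days | Samples to Day 8 | Last sample |
|---|---|---|---|
| Day 8 | 3,5,8; 3,6,8; 4,5,8; 4,6,8; 4,7,8 | 4 | Day 8 |
| Day 9 or 10 | 3,6,9; 4,6,9; 4,7,9; 4,7,10 | 3 | Day 6 or 7 |

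Protocol 3.2.4 reports the Visit 5 samples as Day 8 or 9 without giving the split.

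**Effect of count alone.** The expected maximum of k independent normals is 0.846, 1.029 and 1.163 SD for k = 3, 4 and 5. If all samples sat on a plateau, five against four would give 1.163 - 1.029 = 0.134 SD, and five against three 1.163 - 0.846 = 0.317 SD. For an assumed within-person SD of 0.1-0.3 log10 that is 0.01-0.04 and 0.03-0.10 log10.

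**Effect of count and timing.** Simulated Part 2 minus Part 1 mean nadir for the same true effect, with RNA assumed level by Day 7, flattening, or still falling linearly, a 1.57 log10 fall at Day 8 and within-person SD 0.15-0.25:

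| Part 1 late samples | Part 2 advantage (log10) |
|---|---|
| Days 7 and 8 | about 0.00-0.02 |
| Day 5 or 6, and Day 8 | 0.02-0.14 |
| no Day 8 sample | 0.09-0.50 |

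A second set of runs (1.5 log10 fall, SD 0.1-0.3, including a plateau from Day 5) gave 0.00-0.11 with a Day 8 sample and 0.08-0.48 without. If RNA is level from Day 5, the day of Visit 4 no longer matters, and the advantage with a Day 8 sample is 0.03-0.08.

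**Comparison with the dose effect.** In Protocol Table 1, ED50 = d(1 - e)/e gives 10.9-11.4 mg in every row. At 11.2 mg the shares of maximum effect are 140/151.2 = 92.6% and 200/211.2 = 94.7%, a gap of 2.1 points. For an assumed Emax of 1.7 that is 0.021 x 1.7 = 0.036 log10; for 1.3-2.0 it is 0.03-0.04.

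**Observed cohort means.** Probability that the observed 140 mg mean nadir exceeds the 200 mg mean, n=6 (assumed Emax 1.5 or 2.0):

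| Part 1 participants with a Day 8 sample | Probability |
|---|---|
| same sampling days in both parts | 0.42-0.45 |
| all | 0.43-0.59 |
| half | 0.53-0.84 |
| none | 0.58-0.99 |

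**Fitted curve.** Against a schedule with five samples at every dose, fitted Emax falls by up to 0.15 log10 and ED50 rises by 0.2-1.6 mg. Against matched four-sample nadirs, with all Part 1 Visit 5 samples on Day 8, Emax rises by 0.01-0.10. The estimates move in both comparisons; the sign depends on the reference.

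**The case against.** The strongest reply is that the harm is limited, and much of it stands.

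- A reader might infer that the pooled model could rank 140 mg above 200 mg. It cannot: with a positive effect, the two-parameter Emax curve and the linear fallback both rise with dose, and the exposure models regress on AUC, Cmax or Ctau and do not rank doses. Only observed means and the dose scatter plot (Figure 5.1) can reverse. With n=6 and SD 0.4 the standard error of a two-arm difference is 0.4 x sqrt(2/6) = 0.23 log10, so matched means already reverse 42-45% of the time.
- A reader might place the fault in the Protocol's definition of the nadir. Protocol 10.3.2.2 and 10.3.3.1 contain no Day 8 cut, and through Visit 6 both parts have five samples. The imbalance comes from the SAP rule.
- A reader might infer a fixed bonus for Part 2 from the sample count. Count is the smaller part. The larger effect comes from Part 1 participants seen on Day 9 or 10, and with Part 1 samples on Days 7 and 8 the advantage can be close to zero.
- The models are exploratory, SAP 2.4 states that no formal hypotheses are tested, and change to Day 8 is already listed.

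What the reply does not remove is the unequal sampling, its alignment with dose, the missing term for part, and the SAP's choice of the maximum change as the Emax response.

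**Conclusion.** The point holds as an analysis choice in the SAP that should be changed. The counts (five against three or four) and the direction in favour of 40, 80 and 140 mg follow from the documents. The size does not. It rests on assumed decline shapes, a 1.57 log10 fall, within-person SD 0.15-0.25 and the unreported Part 1 visit days: about 0.00-0.14 log10 with a Day 8 sample and 0.09-0.50 without. That can exceed the roughly 0.04 log10 between 140 and 200 mg implied by Table 1 at Emax about 1.7. The consequence is a shift in fitted Emax and ED50 and a possible reordering of observed means and the scatter plot. The documents do not support a claim that the fitted dose curve reverses, or that Emax is biased in one known direction.

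**What to change.** In SAP 10.1, 10.1.4.1, 11.1 and 11.1.3, make change from baseline to Day 8 the lead response for the pooled dose- and exposure-response models. A single time point has no best-of-k effect.

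Add a rule for Part 1 participants whose Visit 5 was on Day 9 or 10, since they have no Day 8 value and the SAP is silent on them. Interpolate log10 RNA linearly between Visits 4 and 5: L(8) = L(v4) + [(8 - v4)/(v5 - v4)] x [L(v5) - L(v4)]. With visits on Days 6 and 9 the Visit 5 value has weight 2/3. Part 1 dosing ran to Day 10, so both samples are on treatment. Amend the Day 9-11 exclusion in 11.1.2 to allow this use, and align the notes to Table 5.1 and Figure 5.1.

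Report the nadir-to-Day-8 model only as a sensitivity analysis, with the number and days of contributing samples per arm.

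Dropping the Part 2 Day 7 sample is not a substitute. It reverses the bias by 0.02-0.12 log10 where Part 1 Visit 4 was on Day 7, and can leave a gap of up to 0.45 where Visit 5 was on Day 9 or 10.

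The cost is SAP wording and one derived variable. The downsides are an interpolated value for some Part 1 participants, which slightly understates the fall if RNA is flattening, and a little more noise than a nadir.
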